## **9.10 Other Analyses**

A descriptive analysis of the healthcare utilization by patients treated with LR769 will be performed. For this purpose, data will be collected on use of product, number of visits to hospital, days of inpatient hospitalization, use of concomitant medication, and patient's days away from school or work (if applicable) for patient and parent/legal guardian due to bleeding episodes.

## **9.11 Interim Analysis**

One interim analysis will be performed:

- Upon availability of FVIIa plasma activity data for at least 6 patients in each age group, PK profiles along with all safety and efficacy data available at that time will be reviewed by the DMC. Data will be used to identify any unexpected results that may impact safety or efficacy.
- At the time at least 80 bleeding episodes have been treated, data collected will be reviewed to identify any safety or efficacy issues.

The DMC will review these data and make recommendations to continue the study unaltered, or to make any modifications to the study.

## **10 ADMINISTRATIVE CONSIDERATIONS**

### **10.1 Investigators and Study Administrative Structure**

The Sponsor will contract a CRO to perform specific study-related tasks. The division of responsibilities will be documented in mutually agreed documents. Written procedures will be used in order to assure that the study is conducted according to all applicable rules and regulations.

The Principal Investigator will ensure that this study is conducted in accordance with the ethical principles that have their origin in the Declaration of Helsinki and that are consistent with Good Clinical Practice (GCP) and any other local regulations and guidelines.

The Principal Investigator will review all study related documents including the protocol and the current version of the Investigator's Brochure. It is essential that the Principal Investigator be familiar with the protocol and all sections of the Investigator's Brochure prior to initiation of the study.

### **10.2 Institutional Review Board (IRB) or Independent Ethics Committee (IEC) Approval**

A copy of the protocol, Investigator's Brochure, proposed Informed Consent/Assent Form and any other written patient information must be submitted to the IRB/IEC for written approval. A copy of the written IRB/IEC approval of the protocol and Informed Consent/Assent Form must be received by the Sponsor before recruitment of patients into the study and shipment of investigational drug.

The Principal Investigator must submit and, where necessary, obtain approval from the IRB/IEC for all subsequent protocol amendments and changes to the informed consent form. The Principal Investigator should notify the IRB/IEC of deviations from the protocol or SAEs/reportable safety events at the site or reports of such events received from the sponsor in accordance with local procedures.

The Principal Investigator will be responsible for obtaining annual IRB/IEC approval and renewal throughout the duration of the study.

The Principal Investigator will promptly report to the IRB/IEC all changes in research activity and all unanticipated problems involving risks to human patients and will not make any changes in the research without prior Sponsor and IRB/IEC approval, except where necessary to eliminate immediate hazards to human patients.

### **10.3 Ethical Conduct of the Study**

This study will be conducted in compliance with GCP as described in the International Conference on Harmonisation (ICH) document "Guidance for Industry-E6 Good Clinical Practice: Consolidated Guidance" dated April 1996. These practices are consistent with the

principles stated in the Declaration of Helsinki (October 2013 revised version). All other applicable regulations will be adhered to.

## **10.4 Patient Information and Consent**

Written informed consent must be obtained for all patients who are potential study candidates before any study-specific tests or procedures are performed. Parent/legal guardian of the patients who meet general entry criteria will be asked to sign the study-specific, IRB/IEC approved Informed Consent form before any study-specific test or procedures are performed. The written informed consent will be obtained after the context of the study has been fully explained to the patient's parent/legal guardian in a language that is easily understood by the parent/legal guardian. There must also be adequate opportunity to ask questions and have those questions answered to their satisfaction. Study personnel will explain that even if a patient/parent(s)/legal guardians agree to participate in the study and signs an Informed Consent form, the study-specific test or procedures may demonstrate that the patient is not a candidate for the study.

The written informed consent will be prepared in the language(s) of the potential study population and will be administered according to national requirements.

The patient may, depending on his age, receive age-appropriate information as well as asked to sign and date an assent form. Age of providing information and assent form may differ between institutions and will be determined by local law and IRB or IEC requirements.

## **10.5 Patient Confidentiality**

Patient participation is voluntary and patients or his parents/guardians may refuse to participate or withdraw from the study at any time and for any reason. Patients and/or their parents/guardians who participate in the study will be informed that information about them is being entered into a study database and their consent will be obtained and recorded. Patients will be identified only by a patient number and date of birth. They will be informed as to the strict confidentiality of their patient data, and that their medical records may be reviewed for study purposes by authorized individuals other than their treating physician.

## **10.6 Study Monitoring**

Monitoring visits to the Study Sites will be conducted periodically during the study according to the study monitoring plan to ensure that all aspects of the current, approved protocol are being followed. Monitors will be given direct access to original source documents, which will be reviewed for 100% data verification captured in the eCRF. For this study, source documents include but are not limited to the Informed Consent Form, patient's medical records, patient diaries, laboratory results, reports of SAEs, and drug accountability logs. It is important that the investigator and relevant study personnel are available during monitoring visits and audits and that sufficient time is devoted to the process.

## 10.7 Case Report Forms and Study Records

Patient data will be collected both electronically and on paper. The Principal Investigator must ensure the accuracy and completeness of the recorded data and provide his/her signature on the appropriate eCRFs and/or in the electronic system. The Investigator's electronic signature for specific eCRFs will be documented in compliance with ICH/GCP guidelines. Visual and/or computer data review will be performed to identify possible data discrepancies. Data cleaning will be performed on all data in the eCRF. Queries will be created in the data management system and will be issued for appropriate response.

## 10.8 Data Monitoring Committee

The DMC is responsible for the oversight of patient safety. The DMC will consist of three specialists in the care of hemophilia patients. DMC members will be independent of the study and sponsor. During the course of the trial, the DMC will review efficacy, PK, and/or safety data at a minimum of the following timepoints:

- Each serious adverse drug reaction (i.e., an SAE for which at least a possible, probable, or definite causal relationship is assessed by the investigator and/or the sponsor)
- Quarterly: a concise cumulative listing of all SAEs (regardless of relationship to study drug) that occurred in the study
- After interim analysis specified in Section 9.11

The DMC will make recommendations, as appropriate, for study modification or termination because of concerns over patient safety or issues relating to data monitoring or quality control. This will be submitted in writing to the sponsor's Medical Monitor for consideration and final decision. However, if the DMC at any time determines that a potential serious risk exists to patients in the trial, the DMC Chairperson will immediately notify the Sponsor's Medical Monitor per the DMC Charter.

## 10.9 Protocol Deviations

Deviations from clinical protocol requirements will be reviewed and evaluated on an ongoing basis and, as necessary, appropriate corrective actions put into place.

An important subset of protocol deviations is "important protocol deviations," which are defined by ICH E3 as "protocol deviations that may significantly impact the completeness, accuracy, and/or reliability of the study data or that may significantly affect a patient's rights, safety, or well being. For example, *important protocol deviations* may include enrolling patients in deviation of key eligibility criteria designed to ensure a specific patient population or failing to collect data necessary to interpret the primary endpoint, as this may compromise the scientific value of the trial." An example of an important protocol deviation provided in the guideline is "deviations related to entry criteria, conduct of the trial, patient management, or assessment." An analysis of important protocol deviations will be presented in the CSR.

## **10.10 Criteria for Terminating Study**

The sponsor reserves the right to terminate the study at any time, but intends only to exercise this right for valid scientific or administrative reasons and reasons related to patient safety and protection. Investigators and the associated IRB/IEC will be notified in the event of unplanned termination.

Possible reasons for unplanned study termination include but are not limited to:

- The discovery of an unexpected, significant, or unacceptable risk to the patients enrolled in the study.
- A decision on the part of the sponsor to suspend or discontinue development of the investigational product

## **10.11 Criteria for Suspending/Terminating a Study Center**

The sponsor reserves the right to terminate enrollment of patients at a study site at any time after study initiation. Reasons for site termination or suspension include, but are not limited to:

- Non-enrollment of patients
- Significantly slower-than-expected enrollment
- The study site has multiple and/or critical protocol deviations without justification or fails to follow corrective actions
- Failure to obtain/maintain IRB/IEC approval
- Failure to obtain written informed consent
- Failure to report SAE within 24 hours of knowledge
- Failure to enter data in the eCRF in a timely manner
- Loss of, or unaccounted for, investigational product inventory

## **10.12 Access to Source Documentation**

The monitor (or auditors, regulatory inspectors) will check the eCRF form entries against the original source documents. The consent form will include a statement by which the patients allow the monitor/auditor/inspector access to source data (e.g., original laboratory reports etc.) which substantiate information in the eCRF. These personnel, bound by professional confidentiality, will not disclose any personal information.

## **10.13 Data Generation and Analysis**

See the Statistical section of this protocol (Section 9).

## **10.14 Retention of Data**

The investigator/institution will maintain the trial documents as specified in ICH E6 Good Clinical Practice Consolidated Guidance and as required by the applicable regulatory requirement(s). The investigator/institution will take measures to prevent accidental or premature destruction of these documents. If for any reason the Principal Investigator withdraws responsibility for maintaining the trial documents, custody must be transferred to an individual who will assume responsibility. The sponsor must receive written notification of this custodial change.

Essential documents will be retained until at least 2 years after the last approval of a marketing application in an ICH region and until there are no pending or contemplated marketing applications in an ICH region or at least 2 years have elapsed since the formal discontinuation of clinical development of the investigational product. These documents should be retained for a longer period, however, if required by the applicable regulatory requirements or by an agreement with the sponsor.

## **10.15 Financial Disclosure**

All rules and regulation on the documentation and disclosure of any potential financial conflicts will be adhered to.

## **10.16 Publication and Disclosure Policy**

The study will be listed in public databases on clinical studies [www.clinicaltrials.gov](http://www.clinicaltrials.gov) and [www.clinicaltrialsregister.eu](http://www.clinicaltrialsregister.eu). A summary report of the study will be made available after the conclusion of the study. The final report may be submitted to relevant regulatory authorities to support a request for product registration. It is the intention of the sponsor to publish the results of this study in a peer-reviewed journal.

## Appendix 1 Schedule of Events

### Phase A - Initial Safety and PK Phase

Evaluation	Screening Days -21 to -1	Pre-dose	0 min	10 ± 2 min.	30 ± 5 min.	1 hour ± 10 min.	2 hours ± 10 min.	4 hours ± 10 min.	8 hours ± 10 min.
Informed Consent	X								
I/E Criteria	X	X							
Demographics/Medical History	X								
Physical Examination 	X	X							
Clinical Laboratory Tests 	X								
Vital Signs	X	X			X 	X 	X 	X 	X 
Randomization		X							
Drug Administration			X						
Concomitant Medication Assessment	X	X							
AE Assessment	X	X	X	X	X	X	X	X	X
Pharmacokinetic Assessments		X		X 	X 	X 	X 	X 	X 
Immunogenicity Sample 		X							

 See Section 6.3 for physical examination assessments

 See Section 6.5 for clinical laboratory tests; CD4 will only be tested at Screening

 For all patients, regardless whether PK sample is taken

 Depending on assigned sampling schedule (half of the patients sampling schedule 1: at 10±2 minutes, 1 and 4 hours (±10 minutes), and the other half of the patients sampling schedule 2: at 30±5 minutes and 2 and 8 hours (±10 minutes) relative to the start of infusion of study drug)

 Investigator will contact the Medical Monitor regarding any patient who weighs <12 kg for adaptation of the blood sample schedule to the patient's body weight

## Phase B - Treatment of Mild/Moderate Bleeding Episodes

Evaluation	Mild/Moderate Bleeding Episode									
	Pre-treatment	0 hrs	3 hrs	6 hrs	9 hrs	12 hrs	15 hrs	18 hrs	21 hrs	24 hrs
Bleeding Characteristics 	X									
Drug Administration 		X	X 	X 	X	X	X	X	X	
Efficacy Assessment 			X	X	X	X 	X	X	X	X 
Patient Diary 	X	X	X	X	X	X	X	X	X	X
AE Assessment	Throughout Study									
Conmed Assessment	Throughout Study									

 Includes location, date, time of start of bleeding, severity, spontaneous or traumatic

 Exact date, time and dose administered to be noted for each administration

 No study drug administration when in the 225 µg/kg treatment regimen

 Before each (planned) study drug administration and 3 hours after last

 Always to be done, regardless of study drug administration

 By the parent(s)/guardian or other caregiver in conjunction with the patient where possible (e.g., depending on age). Additionally, the site staff will collect their assessment in the patient's records (if applicable).

## Phase B - Treatment of Severe Bleeding Episodes

Evaluation	Severe Bleeding Episode				
	Pre-treatment	0 hrs	q 2 hrs	q 3 hrs	q 4-12 hrs
Bleeding Characteristics 	X				
Drug Administration 		X	X 	X	X
Efficacy assessment 			X	X	X
Patient Diary 	X	X	X	X	X
AE Assessment	X	X	X	X	X
Concomitant Medication Assessment	X	X	X	X	X

 Includes location, date, time of start of bleeding, severity, spontaneous or traumatic

 Exact date, time and dose administered to be noted for each administration. Duration and interval of treatment upon judgment of the treating physician, depending on the type of bleeding

 Prior to each (planned) study drug administration (initially every 2 hours when treated with 75 µg/kg, and at 6 hours after the initial 225 µg/kg administration). In case the treatment is continued beyond 24 hours, efficacy is assessed every 12 hours during the administration of study drug and 12 hours after last study drug administration.

 By patient/caregiver at each study drug administration and efficacy assessment timepoint. Additionally the site staff will collect their assessment in the patient's records (as applicable).

 No study drug administration and efficacy assessment at 2 and 4 hours if assigned to the 225 µg/kg treatment regimen

## Schedule of Events (Phase B Follow-Up Visits)

Evaluation	Following treatment in Phase A					Following 24 weeks visit		End of Study/Early Termination Visit
	3 wks ± 2 days	6 wks ± 5 days	12 wks ± 5 days	18 wks ± 5 days	24 wks ± 5 days	Every 6 wks ± 5 days	Every 12 wks ± 5 days	
Physical Examination 	X 	X 	X 	X 	X	X 	X 	X
Safety Labs (Hematology, chemistry) 			X		X			X
Coagulation 					X 			X 
Adverse Event Assessment	Throughout Study							
Weight		X	X	X	X	X	X	
Vital Signs			X		X		X	X
Health Care Resource Utilization			X		X		X	X
Conmed Assessment	Throughout Study							
Check drug accountability and patient diary	X 	X	X	X	X	X	X	X
Immunogenicity sample 	X	X	X	X	X	X	X	X

 See Section 6.3 for physical examinations

 Inhibitor testing only

 Only check for physical signs of thromboembolic events

 Only check patient diary, no drug accountability

 See Section 6.5.1 for clinical laboratory tests and coagulation tests; CD4 will only be tested at Screening

 Investigator will contact the Medical Monitor regarding any patient who weighs <12 kg for adaptation of the blood sample schedule to the patient's body weight

---

1. INTRODUCTION

This document covers additional analyses to be performed for the protocol LFB-FVIIa-007-14 version 4.0 dated 29 Jun 2016, eCRF dated 07 October 2016, and is considered as an addendum to the main SAP version 2.0 dated 12 September 2017 and Mock TFL's version 2.0 dated 12 September 2017. Due to timelines and planning considerations, the below analyses are intended to be executed post-database lock.

2. ANALYSIS DESCRIPTION

Tables and figures specified in this document will be reported separately from the main output and marked explicitly as addendum tables (see the example in section 3 of this document).

Analyses of the primary efficacy endpoint (Tables 14.2.1.1 through 14.2.2.3 of the main analysis) will be re-run stratifying by age group, using the following strata: <2 years, 2 to <6 years and 6 to <12 years. The same analyses will then be repeated stratifying by BMI, categorized into three classes by tertiles.

Additionally, GEE and GLMM models for primary endpoint will be re-run with PK parameters (e.g., AUC_{last}, AUC_{inf}, and C_{max}), BMI and age group as covariates (see Table 14.2.3.1 as a reference).

The following secondary and tertiary efficacy endpoints will be analyzed stratifying by age groups and BMI using the same categories above.

- Proportion of mild/moderate bleeding episodes successfully treated according to the same criteria as the primary endpoint as per the FDA definition of efficacy, at all other timepoints (see Table 14.2.4.1.1 as reference)
- Proportion of bleeding episodes (mild/moderate only and mild/moderate and severe combined) with a “good” or “excellent” patient (and/or physician when available) reported assessment of efficacy at all timepoints (see Tables 14.2.4.3.1 and 14.2.4.4.1 as reference)
- Time to assessment of a “good” or “excellent” response of the bleeding episodes (mild/moderate only and mild/moderate and severe combined) by the patient (and/or physician when available) (see Tables 14.2.5.1.1 and 14.2.5.2.1 as reference)
- Proportion of bleeding episodes (mild/moderate only and mild/moderate and severe combined) with a “good” or “excellent” physician reported assessment of efficacy at 12 hours (if available) (see Tables 14.2.4.6 and 14.2.4.7 as reference)
- Proportion of recurrences (defined as a bleeding in the same joint/anatomical location within 24 hours after an initial successful response (see Tables 14.2.7.1.1 and 14.2.7.1.2 of the main output as reference)

Time plots for the following parameters will be created, splitting the data by age group (<2 years, 2 to <6 years and 6 to <12 years) and study drug dose:

Addendum Statistical Analysis Plan LFB-FVIIa-007-14

- Proportion of mild/moderate bleeding episodes successfully treated (according to the same criteria as the primary endpoint as per definition for the FDA of efficacy primary efficacy endpoint)
- Proportion of bleeding episodes (mild/moderate and severe, analyzed separately and combined) with a “good” or “excellent” patient (and/or physician when available) reported assessment of efficacy
- Proportion of bleeding episodes still ongoing

The time reported on the plots defined above will be derived as a difference between the time of event (success or end of the bleeding episode) and the time of first study drug injection for the associated bleeding episode.

Additionally, a new analysis summarizing the number of injections required to produce a response (FDA and EMA definition analyzed separately) and time required to reach a response will be conducted. This analysis will also be re-run stratifying by age group using the same thresholds as discussed above. Mock Tables for this analysis can be found in section 3. Time required to reach a response will also be analyzed using the Kaplan-Meier model, as described in the main SAP.

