The null hypothesis will be tested using a one-sided, one-sample, normal approximation test and a test statistic obtained by dividing ( $\hat{p} - 0.55$ ) by its estimated standard error, taking into account the correlation between bleeding episodes for a given patient. The test will be conducted at the 0.0125 level (adjusted from 0.025 to 0.0125 to account for multiplicity of testing). Treatment of mild/moderate bleeding episodes in the study with LR769 of a given dose will be regarded as successful if it is concluded that the true percentage of successfully treated bleeding episodes with that dose is greater than 0.55. The primary endpoint for the FDA is to satisfy the requirements of the US FDA for the evaluation of success.

No imputation of missing data will be performed for the primary analysis of the primary efficacy endpoint. However, two sensitivity analyses will be performed in order to examine the effect of missing data, if any, on the results of the primary analysis. In the first sensitivity analysis, all bleeding episodes for which the value of the primary efficacy endpoint is missing will be assigned as failures. In the second sensitivity analysis, all such bleeding episodes will be assigned as successes.

In addition, the proportions of successfully treated mild/moderate bleeding episodes will be compared between the two LR769 treatment doses at a 2-sided alpha of 0.05.

Two sensitivity analyses based on Generalized estimating equations (GEE) logistic regression analyses and Generalized linear mixed effects models (GLMM) will be used to assess the robustness of the result by accounting for the within-subjects correlation.

The primary efficacy endpoint for the EMA is defined as the proportion of bleeding episodes (mild/moderate and severe combined) with a “good” or “excellent” patient (for mild/moderate bleeding episodes) and physician (for severe bleeding episodes) reported assessment of efficacy at 12 hours after the first administration of study drug. This proportion of success will be evaluated by the EMA as part of the assessment of the benefit risk ratio for each dosing regimen.

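### The SAP addendum repeats the primary analyses in strata of about 12 patients or fewer; if the protocol's normal approximation carries over, the stratum confidence intervals are too narrow

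*SAP*

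**What the plan says.** The addendum, section 2, takes "Analyses of the primary efficacy endpoint (Tables 14.2.1.1 through 14.2.2.3 of the main analysis" and says they "will be re-run stratifying by age group, using the following strata: <2 years, 2 to <6 years and 6 to <12 years". It continues: "The same analyses will then be repeated stratifying by BMI, categorized into three classes by tertiles". Section 1 states that "the below analyses are intended to be executed post-database lock". Section 2 adds that the output "will be reported separately from the main output and marked explicitly as addendum tables".

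Protocol 9.5.1 sets out the primary analysis for each dose. It has a 95% normal-approximation CI, adjusted for within-patient correlation, and a test: "The null hypothesis will be tested using a one-sided, one-sample, normal approximation test". The statistic divides the difference from 0.55 "by its estimated standard error, taking into account the correlation between bleeding episodes for a given patient". On the level: "The test will be conducted at the 0.0125 level (adjusted from 0.025 to 0.0125 to account for multiplicity of testing". The variance estimator is not named.

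Protocol 3.1 plans 12 patients in each of two age ranges, birth to <6 and 6 to <12 years. Protocol 9.1 already provides for analyses by these two groups. The addendum therefore adds a split of the younger group at 2 years, and the BMI tertiles. For the stratum results it gives no small-sample method, no multiplicity handling and no statement that they are descriptive.

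**The concern.** The independent unit is the patient, not the bleed. A cluster-adjusted standard error from 4, 8 or 12 patients is itself poorly estimated, and a normal reference ignores that. The interval is then too short and the test rejects too often. The strata are small on the plan's own numbers, and the addendum does not say how they are to be read.

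The practical risk is over-reading. An addendum table for the youngest children with a lower limit above 0.55 would look like evidence that the performance criterion is met in that group, when the limit is tighter than the data support. Marking a table as an addendum separates it from the main output but does not correct its interval.

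**Working it through.** **Inputs from the protocol.** Section 9.2: criterion 0.55, assumed true success 0.70, within-patient correlation 0.1, 22 patients, 352 episodes, 8 episodes per patient per dose, one-sided alpha 0.0125. Section 3.1: 12 patients per age range.

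**Stratum sizes.** The 6 to <12 group has about 12 patients. BMI tertiles of 24 give 24/3 = 8. The two younger strata share about 12, and the split at 2 years is not stated. I assume 4 under 2 years. Protocol 6.5 sets a 10.5 kg minimum for children under 12 kg bled by peripheral venipuncture, which makes a small stratum plausible.

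**The plan's own figure.** Design effect = 1 + (8 − 1) × 0.1 = 1.7. Effective n per dose = 22 × 8 / 1.7 = 103.5. Null SE = √(0.55 × 0.45/103.5) = 0.0489. Alternative SE = √(0.70 × 0.30/103.5) = 0.0450. Critical z = 2.241.
- Power with the null SE = Φ((0.15 − 2.241 × 0.0489)/0.0450) = 81.5%.
- Power with the Wald SE = Φ(0.15/0.0450 − 2.241) = 86.2%.

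The stated power of at least 80% reproduces.

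**One-sided error in a stratum.** Beta-binomial bleeds were simulated at a true rate of 0.55 with correlation 0.1 (200,000 runs per setting). With K patients, the cluster-robust variance is K/(K − 1) × Σ(xᵢ − p̂mᵢ)² / n², where xᵢ and mᵢ are the successes and bleeds of patient i and n is the total number of bleeds. The test rejects when (p̂ − 0.55)/SE exceeds the critical value for nominal 0.0125. Uneven counts are skewed with a mean of 8. Multiples of nominal are in brackets.

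| Method | 4 patients | 6 | 8 | 12 | 24 |
|---|---|---|---|---|---|
| Robust SE, z, equal counts | 0.059 (4.7) | 0.045 (3.6) | 0.036 (2.9) | 0.027 (2.1) | 0.019 (1.6) |
| Robust SE, z, uneven counts | 0.092 (7.4) | 0.066 (5.3) | 0.053 (4.2) | 0.040 (3.2) | 0.027 (2.2) |
| Estimated-ICC Wald SE, z, equal | 0.037 (3.0) | 0.033 (2.6) | 0.028 (2.3) | 0.024 (1.9) | 0.019 (1.5) |
| Estimated-ICC null SE, z, equal | 0.027 (2.2) | 0.019 (1.5) | 0.019 (1.5) | 0.019 (1.5) | 0.016 (1.3) |
| Robust SE, t(K − 1), equal | 0.013 (1.0) | 0.015 (1.2) | 0.017 (1.3) | 0.015 (1.2) | 0.014 (1.1) |
| Robust SE, t(K − 1), uneven | 0.028 (2.3) | 0.029 (2.3) | 0.028 (2.3) | 0.025 (2.0) | 0.021 (1.7) |

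An analytic check, P(t(K − 1) > 2.241), gives 0.055, 0.038, 0.030 and 0.023 for 4, 6, 8 and 12 patients, close to the first row.

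**Coverage of the nominal 95% interval** (robust SE, true rate 0.70, correlation 0.1):

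| Reference and counts | 4 patients | 8 | 12 |
|---|---|---|---|
| z, equal counts | 85% | 90.5% | 92% |
| z, uneven counts | 78% | 86% | 89% |

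A t(K − 1) reference gives about 93 to 95% with equal counts and 90 to 92% with uneven counts. The t interval is wider than the z interval by a factor of 1.62 with 4 patients, 1.21 with 8 and 1.12 with 12.

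**The case against.** The strongest reply is that much of this is inferred. The tables to be re-run are defined in the main SAP, which is not among the documents supplied. That the test against 0.55 is repeated in each stratum follows only from the instruction to re-run, and a small-sample method in the main SAP cannot be ruled out. The variance estimator is unnamed, and some choices give milder inflation. The under-2 size is an assumption. The 6 to <12 group was already a protocol subgroup. All of this stands, and it makes the finding conditional.

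It does not remove the finding. The 95% interval belongs to the same primary analysis in Protocol 9.5.1, so the shortfall in coverage applies whether or not a p-value is printed. Every estimated-variance z method in the table exceeds nominal at every stratum size.

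A reader might go further and infer that the addendum creates 12 formal tests (6 strata × 2 doses) with a large chance of some false success. If 12 tests were independent and each held 0.0125, that chance would be 1 − 0.9875¹² = 14%, and more with inflated tests. The documents do not support treating this as a family error rate. Protocol 9.5.1 attaches success to a dose in the study as a whole, not to a stratum. The age and BMI strata reuse the same patients. The output is kept separate and labelled.

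A reader might also put all the inflation down to stratification. The same robust z test on all 24 patients already runs at about 1.6 times nominal.

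**Conclusion.** The point holds in a limited form. If the stratum analyses follow Protocol 9.5.1, their intervals are too narrow: moderately so with 8 to 12 patients, and markedly so with about 4. Any repeated one-sided test would run at about 2 to 5 times nominal with a cluster-robust SE and equal counts, about 3 to 7 times with uneven counts, and about 1.5 to 3 times with an estimated-ICC SE and equal counts. Uneven counts are the likelier case, since Protocol 3.1.2.2 sets no limit on treated bleeds per patient.

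These figures assume correlation 0.1, a mean of 8 bleeds per patient per dose, 24 patients analysed and 4 under 2 years. A smaller youngest stratum would be worse. The documents do not support reading this as a flaw in the power statement, or as a plan to claim efficacy by stratum. It is a risk of over-reading subgroup intervals, and it is cheap to remove.

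**What to change.** In addendum section 2:
- State that results by age stratum and BMI tertile are descriptive estimates, with no test against 0.55.
- Show the number of patients and bleeds beside each estimate.
- Name the variance estimator, and form cluster-adjusted CIs with a t reference on patients in the stratum minus 1 degrees of freedom.
- Add a note that, with uneven bleed counts, these intervals may still cover only about 90 to 92%.

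For differences by age or BMI, rely on the age-group and BMI terms in the GEE and GLMM models that the addendum already re-runs. An age-by-regimen interaction would not serve, because it asks whether the difference between doses varies with age, not whether success does.

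The cost is a paragraph of wording and a change of reference distribution. The downside is wider subgroup intervals, by the factors shown above.
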